#### **6.2.2.2 Disease Parameters**

Measurable disease: Measurable lesions are defined as those that can be accurately

measured in at least one dimension (longest diameter to be recorded) as  $\geq 20$  mm by chest x-ray, as  $\geq 10$  mm with CT scan, or  $\geq 10$  mm with calipers by clinical exam. All tumor measurements must be recorded in millimeters (or decimal fractions of centimeters).

**Malignant lymph nodes.** To be considered pathologically enlarged and measurable, a lymph node must be  $\geq 15$  mm in short axis when assessed by CT scan (CT scan slice thickness recommended to be no greater than 5 mm). At baseline and in follow-up, only the short axis will be measured and followed.

**Non-measurable disease.** All other lesions (or sites of disease), including small lesions (longest diameter  $<10$  mm or pathological lymph nodes with  $\geq 10$  to  $<15$  mm short axis), are considered non-measurable disease. Bone lesions, leptomeningeal disease, ascites, pleural/pericardial effusions, lymphangitis cutis/pulmonitis, inflammatory breast disease, and abdominal masses (not followed by CT or MRI), are considered as non-measurable.

**Note:** Cystic lesions that meet the criteria for radiographically defined simple cysts should not be considered as malignant lesions (neither measurable nor non-measurable) since they are, by definition, simple cysts.

‘Cystic lesions’ thought to represent cystic metastases can be considered as measurable lesions, if they meet the definition of measurability described above. However, if non-cystic lesions are present in the same patient, these are preferred for selection as target lesions.

**Target lesions.** All measurable lesions up to a maximum of 2 lesions per organ and 5 lesions in total, representative of all involved organs, should be identified as **target lesions** and recorded and measured at baseline. Target lesions should be selected on the basis of their size (lesions with the longest diameter), be representative of all involved organs, but in addition should be those that lend themselves to reproducible repeated measurements. It may be the case that, on occasion, the largest lesion does not lend itself to reproducible measurement in which circumstance the next largest lesion which can be measured reproducibly should be selected. A sum of the diameters (longest for non-nodal lesions, short axis for nodal lesions) for all target lesions will be calculated and reported as the baseline sum diameters. If lymph nodes are to be included in the sum, then only the short axis is added into the sum. The baseline sum diameters will be used as reference to further characterize any objective tumor regression in the measurable dimension of the disease.

**Non-target lesions.** All other lesions (or sites of disease) including any measurable lesions over and above the 5 target lesions should be identified as **non-target lesions** and should also be recorded at baseline. Measurements of these lesions are not required, but the presence, absence, or in rare cases unequivocal progression of each should be noted throughout follow-up.

#### 6.2.2.3 Methods for Evaluation of Measurable Disease

All measurements should be taken and recorded in metric notation using a ruler or calipers. All baseline evaluations should be performed as closely as possible to the beginning of treatment and never more than 4 weeks before the beginning of the treatment.

The same method of assessment and the same technique should be used to characterize each identified and reported lesion at baseline and during follow-up. Imaging-based evaluation is preferred to evaluation by clinical examination unless the lesion(s) being followed cannot be imaged but are assessable by clinical exam.

**Clinical lesions:** Clinical lesions will only be considered measurable when they are superficial (e.g., skin nodules and palpable lymph nodes) and  $\geq 10$  mm diameter as assessed using calipers (e.g., skin nodules). In the case of skin lesions, documentation by color photography, including a ruler to estimate the size of the lesion, is recommended.

**Chest x-ray:** Lesions on chest x-ray are acceptable as measurable lesions when they are clearly defined and surrounded by aerated lung. However, CT is preferable.

**Conventional CT and MRI:** This guideline has defined measurability of lesions on CT scan based on the assumption that CT slice thickness is 5 mm or less. If CT scans have slice thickness greater than 5 mm, the minimum size for a measurable lesion should be twice the slice thickness. MRI is also acceptable in certain situations (e.g. for body scans).

Use of MRI remains a complex issue. MRI has excellent contrast, spatial, and temporal resolution; however, there are many image acquisition variables involved in MRI, which greatly impact image quality, lesion conspicuity, and measurement. Furthermore, the availability of MRI is variable globally. As with CT, if an MRI is performed, the technical specifications of the scanning sequences used should be optimized for the evaluation of the type and site of disease. Furthermore, as with CT, the modality used at follow-up should be the same as was used at baseline and the lesions should be measured/assessed on the same pulse sequence. It is beyond the scope of the RECIST guidelines to prescribe specific MRI pulse sequence parameters for all scanners, body parts, and diseases. Ideally, the same type of scanner should be used and the image acquisition protocol should be followed as closely as possible to prior scans. Body scans should be performed with breath-hold scanning techniques, if possible.

**PET-CT:** At present, the low dose or attenuation correction CT portion of a combined PET-CT is not always of optimal diagnostic CT quality for use with RECIST measurements. However, if the site can document that the CT performed as part of a PET-CT is of identical diagnostic quality to a diagnostic CT (with IV and oral contrast), then the CT portion of the PET-CT can be used for RECIST measurements and can be used interchangeably with conventional CT in accurately measuring cancer lesions over time. Note, however, that the PET portion of the CT introduces additional data which may bias an investigator if it is not routinely or serially performed.

**Ultrasound:** Ultrasound is not useful in assessment of lesion size and should not be used as a method of measurement. Ultrasound examinations cannot be reproduced in their entirety for independent review at a later date and, because they are operator dependent, it cannot be guaranteed that the same technique and measurements will be taken from one assessment to the next. If new lesions are identified by ultrasound in the course of the study, confirmation by CT or MRI is advised. If there is concern about radiation exposure at CT, MRI may be used instead of CT in selected instances.

**Endoscopy, Laparoscopy:** The utilization of these techniques for objective tumor evaluation is not advised. However, such techniques may be useful to confirm complete pathological response when biopsies are obtained or to determine relapse in trials where recurrence following complete response (CR) or surgical resection is an endpoint.

**Tumor markers:** Tumor markers alone cannot be used to assess response. If markers are initially above the upper normal limit, they must normalize for a patient to be considered in

complete clinical response. Specific guidelines for both CA-125 response (in recurrent ovarian cancer) and PSA response (in recurrent prostate cancer) have been published (71-73). In addition, the Gynecologic Cancer Intergroup has developed CA-125 progression criteria which are to be integrated with objective tumor assessment for use in first-line trials in ovarian cancer (74).

**Cytology, Histology:** These techniques can be used to differentiate between partial responses (PR) and complete responses (CR) in rare cases (e.g., residual lesions in tumor types, such as germ cell tumors, where known residual benign tumors can remain).

The cytological confirmation of the neoplastic origin of any effusion that appears or worsens during treatment when the measurable tumor has met criteria for response or stable disease is mandatory to differentiate between response or stable disease (an effusion may be a side effect of the treatment) and progressive disease.

**FDG-PET:** While FDG-PET response assessments need additional study, it is sometimes reasonable to incorporate the use of FDG-PET scanning to complement CT scanning in assessment of progression (particularly possible 'new' disease). New lesions on the basis of FDG-PET imaging can be identified according to the following algorithm:

- a. Negative FDG-PET at baseline, with a positive FDG-PET at follow-up is a sign of PD based on a new lesion.
- b. No FDG-PET at baseline and a positive FDG-PET at follow-up: If the positive FDG-PET at follow-up corresponds to a new site of disease confirmed by CT, this is PD. If the positive FDG-PET at follow-up is not confirmed as a new site of disease on CT, additional follow-up CT scans are needed to determine if there is truly progression occurring at that site (if so, the date of PD will be the date of the initial abnormal FDG-PET scan). If the positive FDG-PET at follow-up corresponds to a pre-existing site of disease on CT that is not progressing on the basis of the anatomic images, this is not PD.
- c. FDG-PET may be used to upgrade a response to a CR in a manner similar to a biopsy in cases where a residual radiographic abnormality is thought to represent fibrosis or scarring. The use of FDG-PET in this circumstance should be prospectively described in the protocol and supported by disease-specific medical literature for the indication. However, it must be acknowledged that both approaches may lead to false positive CR due to limitations of FDG-PET and biopsy resolution/sensitivity.

Note: A 'positive' FDG-PET scan lesion means one which is FDG avid with an uptake greater than twice that of the surrounding tissue on the attenuation corrected image.

#### 6.2.2.4 Evaluation of Target Lesions

**Complete Response (CR):** Disappearance of all target lesions. Any pathological lymph nodes (whether target or non-target) must have reduction in short axis to <10 mm.

**Partial Response (PR):** At least a 30% decrease in the sum of the diameters of target lesions, taking as reference the baseline sum diameters.

**Progressive Disease (PD):** At least a 20% increase in the sum of the diameters of target lesions, taking as reference the smallest sum on study (this includes the baseline sum if that is the smallest on study). In addition to the relative increase of 20%, the sum must also demonstrate an absolute increase of at least 5 mm. (Note: the appearance of one or more

new lesions is also considered progressions).

**Stable Disease (SD):** Neither sufficient shrinkage to qualify for PR nor sufficient increase to qualify for PD, taking as reference the smallest sum diameters while on study.

#### 6.2.2.5 Evaluation of Non-Target Lesions

**Complete Response (CR):** Disappearance of all non-target lesions and normalization of tumor marker level. All lymph nodes must be non-pathological in size (<10 mm short axis).

Note: If tumor markers are initially above the upper normal limit, they must normalize for a patient to be considered in complete clinical response.

**Non-CR/Non-PD:** Persistence of one or more non-target lesion(s) and/or maintenance of tumor marker level above the normal limits.

**Progressive Disease (PD):** Appearance of one or more new lesions and/or *unequivocal progression* of existing non-target lesions. *Unequivocal progression* should not normally trump target lesion status. It must be representative of overall disease status change, not a single lesion increase.

Although a clear progression of “non-target” lesions only is exceptional, the opinion of the treating physician should prevail in such circumstances, and the progression status should be confirmed at a later time by the review panel (or Principal Investigator).

#### 6.2.2.6 Evaluation of Best Overall Response

The best overall response is the best response recorded from the start of the treatment until disease progression/recurrence (taking as reference for progressive disease the smallest measurements recorded since the treatment started). The patient's best response assignment will depend on the achievement of both measurement and confirmation criteria.

#### For Patients with Measurable Disease (i.e., Target Disease)

Target Lesions	Non-Target Lesions	New Lesions	Overall Response	Best Overall Response when Confirmation is Required*
CR	CR	No	CR	$\geq 4$ wks. Confirmation**
CR	Non-CR/Non-PD	No	PR	$\geq 4$ wks. Confirmation**
CR	Not evaluated	No	PR	
PR	Non-CR/Non-PD/not evaluated	No	PR	
SD	Non-CR/Non-PD/not evaluated	No	SD	Documented at least once $\geq 4$ wks. from baseline**
PD	Any	Yes or No	PD	no prior SD, PR or CR
Any	PD***	Yes or No	PD	
Any	Any	Yes	PD	

\* See RECIST 1.1 manuscript for further details on what is evidence of a new lesion.

Target Lesions	Non-Target Lesions	New Lesions	Overall Response	Best Overall Response when Confirmation is Required*
** Only for non-randomized trials with response as primary endpoint.				
*** In exceptional circumstances, unequivocal progression in non-target lesions may be accepted as disease progression.				
Note: Patients with a global deterioration of health status requiring discontinuation of treatment without objective evidence of disease progression at that time should be reported as “ symptomatic deterioration .” Every effort should be made to document the objective progression even after discontinuation of treatment.				

### For Patients with Non-Measurable Disease (i.e., Non-Target Disease)

Non-Target Lesions	New Lesions	Overall Response
CR	No	CR
Non-CR/non-PD	No	Non-CR/non-PD*
Not all evaluated	No	not evaluated
Unequivocal PD	Yes or No	PD
Any	Yes	PD

\* ‘Non-CR/non-PD’ is preferred over ‘stable disease’ for non-target disease since SD is increasingly used as an endpoint for assessment of efficacy in some trials so to assign this category when no lesions can be measured is not advised

#### 6.2.2.7 Duration of Response

Duration of overall response: The duration of overall response is measured from the time measurement criteria are met for CR or PR (whichever is first recorded) until the first date that recurrent or progressive disease is objectively documented (taking as reference for progressive disease the smallest measurements recorded since the treatment started).

The duration of overall CR is measured from the time measurement criteria are first met for CR until the first date that progressive disease is objectively documented.

Duration of stable disease: Stable disease is measured from the start of the treatment until the criteria for progression are met, taking as reference the smallest measurements recorded since the treatment started, including the baseline measurements.

#### 6.2.3 Non-Hodgkin’s Lymphoma

Response and progression for non-Hodgkin’s lymphoma will be evaluated in this study using the International Working Group Recommendations ([75](#)).

#### Complete Response (CR) requires the following:

- Complete disappearance of all detectable clinical evidence of disease and disease-related symptoms if present before therapy.
- Typically FDG-avid lymphoma: in patients with no pretreatment PET scan or when the PET scan was positive before therapy, a post-treatment residual mass of any size is permitted as long as it is PET negative.

- Variably FDG-avid lymphomas/FDG avidity unknown: in patients without a pretreatment PET scan, or if a pretreatment PET scan was negative, all lymph nodes and nodal masses must have regressed on CT to normal size ( $\leq 1.5$  cm in their greatest transverse diameter for nodes  $> 1.5$  cm before therapy). Previously involved nodes that were 1.1 to 1.5 cm in their long axis and more than 1.0 cm in their short axis before treatment must have decreased to  $\leq 1.0$  cm in their short axis after treatment.
- The spleen and/or liver, if considered enlarged before therapy on the basis of a physical examination or CT scan, should not be palpable on physical examination and should be considered normal size by imaging studies, and nodules related to lymphoma should disappear. However, determination of splenic involvement is not always reliable because a spleen considered normal in size may still contain lymphoma, whereas an enlarged spleen may reflect variations in anatomy, blood volume, the use of hematopoietic growth factors, or causes other than lymphoma.
- If the bone marrow was involved by lymphoma before treatment, the infiltrate must have cleared on repeat bone marrow biopsy. The biopsy sample on which this determination is made must be adequate (with a goal of  $> 20$  mm unilateral core). If the sample is indeterminate by morphology, it should be negative by immunohistochemistry. A sample that is negative by immunohistochemistry but that demonstrates a small population of clonal lymphocytes by flow cytometry will be considered a CR until data become available demonstrating a clear difference in patient outcome.

**Partial Response (PR) requires:**

- At least a 50% decrease in sum of the product of the diameters (SPD) of up to six of the largest dominant nodes or nodal masses. These nodes or masses should be selected according to all of the following: they should be clearly measurable in at least 2 perpendicular dimensions; if possible they should be from disparate regions of the body; and they should include mediastinal and retroperitoneal areas of disease whenever these sites are involved.
- No increase should be observed in the size of other nodes, liver, or spleen.
- Splenic and hepatic nodules must regress by  $\geq 50\%$  in their SPD or, for single nodules, in the greatest transverse diameter.
- With the exception of splenic and hepatic nodules, involvement of other organs is usually assessable and no measurable disease should be present.
- Bone marrow assessment is irrelevant for determination of a PR if the sample was positive before treatment. However, if positive, the cell type should be specified (e.g., large-cell lymphoma or small neoplastic B cells). Patients who achieve a CR by the above criteria, but who have persistent morphologic bone marrow involvement will be considered partial responders.

When the bone marrow was involved before therapy and a clinical CR was achieved, but with no bone marrow assessment after treatment, patients should be considered partial responders.

- No new sites of disease should be observed.
- Typically, FDG-avid lymphoma: for patients with no pretreatment PET scan or if the PET scan was positive before therapy, the post-treatment PET should be positive in at least one previously involved site. Variably FDG-avid lymphomas/FDG-avidity unknown: for patients without a pretreatment PET scan, or if a pretreatment PET scan was negative, CT

criteria should be used.

**Stable disease is defined as less than a PR (see above) but is not progressive disease (see below):**

- A patient is considered to have SD when he or she fails to attain the criteria needed for a CR or PR, but does not fulfill those for progressive disease (see Relapsed Disease [after CR]/Progressive Disease [after PR, SD]).
- Typically, FGD-avid lymphomas: the PET should be positive at prior sites of disease with no new areas of involvement on the post-treatment CT or PET.
- Variably FDG-avid lymphomas/FDG-avidity unknown: for patients without a pretreatment PET scan or if the pretreatment PET was negative, there must be no change in the size of the previous lesions on the post-treatment CT scan.

**Relapsed disease (after CR)/Progressive disease (after PR/SD) requires the following:**

- Appearance of any new lesion more than 1.5 cm in any axis during or at the end of therapy, even if other lesions are decreasing in size. Increased FDG uptake in a previously unaffected site should only be considered relapsed or progressive disease after confirmation with other modalities. In patients with no prior history of pulmonary lymphoma, new lung nodules identified by CT are mostly benign. Thus, a therapeutic decision should not be made solely on the basis of the PET without histologic confirmation.
- At least a 50% increase from nadir in the SPD of any previously involved nodes, or in a single involved node, or the size of other lesions (e.g., splenic or hepatic nodules). To be considered progressive disease, a lymph node with a diameter of the short axis of less than 1.0 cm must increase by  $\geq 50\%$  and to a size of  $1.5 \times 1.5$  cm or more than 1.5 cm in the long axis.
- At least a 50% increase in the longest diameter of any single previously identified node more than 1 cm in its short axis.
- Lesions should be PET positive if observed in a typical FDG-avid lymphoma or the lesion was PET positive before therapy unless the lesion is too small to be detected with current PET systems (< 1.5 cm in its long axis by CT).

#### 6.2.4 Time to Progression

Time to progression will be measured from the date of protocol consent until death of progressive disease is documented.

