Patients receiving the 10-day treatment schedule without evidence of an ongoing response after any 2 consecutive cycles of treatment will discontinue rhIL-15 and be followed until disease progression is documented or they go off study for another reason. (Ongoing response is defined as: > 15% decrease in sum of marker lesions and/or improvement or disappearance of some non-measurable lesions and/or > 10% decrease in tumor markers.) Patients receiving the 5-day treatment schedule will have 4 cycles of treatment to demonstrate responsiveness to rhIL-15, so that patients are given an equal number of rhIL-15 doses to confirm the treatment has sufficient activity to justify more prolonged treatment.

Patients who demonstrate a complete response (CR) to treatment will receive 2 additional cycles after the cycle where the CR is first documented.

Patients whose best response after 2 consecutive cycles of treatment is stable disease and those who stop treatment due to toxicity will be followed with routine exams and restaging x-rays (every 60 days x 3 and then quarterly) unless progressive disease is documented or they begin another treatment for their cancer.

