### 3.8 STUDY CALENDARS

#### 3.8.1 10 Day Schedule

Procedure	Pre-treatment		Day on Treatment (For All Cycles  )											During-treatment			Follow-Up Period 	End of Study 
	Screening	Baseline 	1	2	3	4	5	6	7	8	9	10	11	12 	21-27	28-34		
CIV rhIL-15 treatment 			x	x	x	x	x	x	x	x	x	x	x					
Pathology confirmed	x																	
Performance status	x	x	x						x							x	x	x
History & physical exam 	x	x	x	x	x	x	x	x	x	x	x	x	x		x	x	x	
Vital Signs  and Weight	x	x	x	x	x	x	x	x	x	x	x	x	x		x	x	x	
Acute Care, Hepatic and Mineral Panels and LDH	x			x	x	x	x	x	x	x	x	x	x		x	x	x	
Ammonia level	x			x										x				
I/Os				x	x	x	x	x	x	x	x	x	x	x	x	x		
CBC w/differential,	x	x	x	x	x	x	x	x	x	x	x	x	x	x	x	x	x	x
Reticulocyte Count		x																
Hepatitis and HIV serology	x																	
Thyroid function panel	x															x		
Troponin T		x	x				x							x		x		
Urinalysis	x																	
EKG	x		x									x			x			
Pulmonary function tests	x																	
HLA (A, B, C, DR, DQ) typing		x																
Tumor imaging and serum tumor markers 	x	x													x 	x		
Serum $\beta$ HCG 	x		x															
ANA, RF and anti-thyroid antibodies	x															x		
Pharmacokinetics (PK) 			x	x	x			x	x	x	x	x	x					
Serum immunoglobulin levels		x																
Flow cytometry ([name] Lab) 		x	x					x				x		x	x	x		
Flow cytometry ([name] Lab) 		x	x					x				x		x	x	x		
Cytokine and MesoScale inflammatory cytokines 			x	x				x				x						
Anti-IL-15 antibodies 			x									x		x	x	x	x	
Optional Tumor Biopsy 		x										x						

1. Cycles 1 and 2 for the 10-day dosing schedule will be 42 days in length, but subsequent cycles will be 28 days in length with all cycles allowing an additional 7 days allowed for reasons other than recovery for treatment-related toxicities.
2. Day 12 tests and procedures only occur on Cycle 1.
3. Patients whose best response after 2 consecutive cycles of treatment is stable disease will be followed with routine exams and restaging scans: Every 60 days x 3; then quarterly for up to 2 years after starting treatment unless progressive disease is documented, or they begin another treatment for their cancer.
4. Denotes testing to be performed at an end of study visit (just prior to the patient being taken off study), if feasible.

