### 3.8.2 5 Day Schedule

Procedure	Pre-treatment		Days During-treatment 							After treatment			
	Screening	Baseline 	1	2	3	4	5	6	8	21±4 	End of Treatment 	Follow-Up Period 	End of Study 
CIV rhIL-15 treatment 			x	x	x	x	x	x 					
Pathology confirmed	x												
Performance status	x	x	x						x		x	x	x
History & physical exam 	x	x	x	x	x	x	x	x	x		x	x	x
Vital Signs  and Weight	x	x	x	x	x	x	x	x	x		x	x	x
NIH Advance Directives Form 													
Acute Care, Hepatic and Mineral Panels and LDH	x	x	x	x	x	x	x	x	x	x	x	x	x
Ammonia level	x		x						x				
I/Os			x	x	x	x	x	x	x				
CBC w/differential	x	x	x	x	x	x	x	x	x	x	x	x	x
Reticulocyte Count		x											
Hepatitis and HIV serology	x												
Thyroid function tests: TSH and T4	x									x	x		
Troponin T or I, based on availability of test in DLM		x	x										
Urinalysis	x												
EKG	x		x										
Pulmonary function tests	x												
HLA (A, B, C, DR, DQ) typing		x											
Tumor imaging and serum tumor markers 	x	x									x		
Serum βHCG 	x		x										
ANA, RF and anti-thyroid antibodies	x										x		
Pharmacokinetics (PK) 			x	x	x	x	x	x					
Serum immunoglobulin levels		x											
Flow cytometry ([name] Lab) 		x	x						x	x			
Flow cytometry ([name] Lab) 		x	x						x	x			
Cytokine and MesoScale inflammatory cytokines 			x	x	x	x	x	x	x	x			
Anti-IL-15 antibodies 			x							x		x	
Optional Tumor Biopsies 		x							x				

**Abbreviated Title:** Ph I Study of CIV rhIL-15

**Version Date:** 06/13/2018

1. All cycles are 21 days in length, but the end of cycle evaluations may be performed  $\pm$  4 days from this time point and an additional 7 days allowed for reasons other than recovery for treatment-related toxicities. Cycle 1 day 21 and cycle 2 day 1 maybe the same calendar day for certain patients. This also applies to later cycles where day 21 of a previous cycle falls on the same calendar day as day 1 of the subsequent cycle.
2. Patients whose best response after 4 consecutive cycles of treatment is stable disease will be followed with routine exams and restaging scans: Every 60 days x 3; then quarterly for up to 2 years after starting treatment unless progressive disease is documented, or they begin another treatment for their cancer.

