### **3.10 CRITERIA FOR REMOVAL FROM THE PROTOCOL THERAPY AND OFF-STUDY CRITERIA**

Prior to documenting removal from study, effort must be made to have all subjects complete a safety visit approximately 30 days following the last dose of study therapy.

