#### **3.10.2 Off-Study Criteria**

- Voluntary withdrawal of consent by the patient to participate in the study
- Patient non-compliance with treatment and research plans
- Initiation of another anticancer treatment
- Any new medical or psychiatric condition that, in the opinion of the PI, precludes the safe continuation of the study
- Death

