### 7.3 IND SPONSOR REPORTING CRITERIA

During the first 30 days after the subject receives investigational agent/intervention, the investigator must **immediately** report to the sponsor, using the mandatory MedWatch form 3500a, any serious adverse event, whether or not considered drug related, including those listed in the protocol or investigator brochure and must include an assessment of whether there is a reasonable possibility that the drug caused the event. For serious adverse events that occur more than 30 days after the last administration of investigational agent/intervention, only report those that have an attribution of at least possibly related to the agent/intervention.

Required timing for reporting per the above guideline:

- Deaths (except death due to progressive disease) must be reported via email within 24 hours. A complete report must be submitted within one business day.
- Other serious adverse events including deaths due to progressive disease must be reported within one business day

Events will be submitted to the Center for Cancer Research (CCR) at: [[contact]](mailto:[contact]) and to the CCR PI and study coordinator.

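### Section 6.2.4 ends time to progression at death from progressive disease; the likeliest intended wording defines progression-free survival, so event and label must be reconciled

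*Combined protocol and SAP*

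**What the plan says.** Section 1.1.2 names response rate and TTP as the two measures of antitumor activity. Section 8 repeats both and calls every secondary evaluation exploratory, but gives no origin, event or censoring rule for TTP. The only definition is in 6.2.4: "Time to progression will be measured from the date of protocol consent until death of progressive disease is documented".

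The follow-up plan is built around progression:

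- Section 3.1: 10-day patients without an ongoing response "will discontinue rhIL-15 and be followed until disease progression is documented or they go off study for another reason".
- Section 3.8.1, footnote 3: "Patients whose best response after 2 consecutive cycles of treatment is stable disease will be followed with routine exams and restaging scans", with an end point at progression or new treatment.
- Section 3.8.2, footnote 2, for the 5-day schedule: scans every 60 days three times, then "quarterly for up to 2 years after starting treatment unless progressive disease is documented, or they begin another treatment for their cancer".
- Section 3.10.2 lists death and "Initiation of another anticancer treatment" among the reasons for leaving the study.

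Two related definitions start at treatment rather than at consent: best overall response (6.2.2.6) and, for solid tumors, the duration of stable disease in 6.2.2.7: "Stable disease is measured from the start of the treatment until the criteria for progression are met".

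**The concern.** An endpoint called time to progression should have progression as its event. As printed, the event is death from progressive disease. An analyst who follows the sentence would not stop the clock at a progression scan. An analyst who repairs it must decide, without help from the protocol, whether a death without documented progression is an event. The reported quantity could therefore be TTP or PFS, and the choice could be made after the data are seen.

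The origin is a smaller matter. Counting from consent gives a solid-tumor patient with stable disease and then progression two different durations for one course, and it adds time before any drug was given.

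**Working it through.** The plan states no median, event count, power or threshold for TTP, so there is no figure to reproduce.

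**1. The event under each reading.** The last column applies the censoring rule proposed under the fix, because the plan has none.

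| Patient's course | As printed | With 'or' (PFS) | TTP proper |
|---|---|---|---|
| Progression on scan, later cancer death | Event at death, if known | Event at progression | Event at progression |
| Progression on scan, leaves study alive | No event | Event at progression | Event at progression |
| Death from another cause, no progression seen | No event | Event at death | Censored |
| Cancer death before any scan shows progression | Event at death | Event at death | Censored |
| Alive without progression | No event | Censored | Censored |

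The printed reading departs from both alternatives in the first two rows, which are the ordinary course in this population. The two repaired readings differ only for patients who die without documented progression (rows three and four).

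**2. Fit with data collection.** Scheduled scans and examinations stop at progression or new treatment (3.1; 3.8.1 footnote 3; 3.8.2 footnote 2). After progression the plan asks for a visit to "complete a safety visit approximately 30 days following the last dose of study therapy" (3.10) and, if feasible, an end-of-study visit. It schedules no survival follow-up. The schedule suits progression as the event and does not suit cancer death.

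**3. The origin.** If progression is the event:

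Time from consent = time from first dose + consent-to-dose lag.

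The documents do not give the lag. The values 0, 7 and 28 days are assumptions for illustration: 7 days borrows the catheter-placement window (3.6.6) and 28 days the baseline-test window (2.4). Neither window says when consent is signed.

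Share of recorded time = lag / (elapsed days + lag), where elapsed days = study day − 1 and cycles are not delayed.

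- **5-day schedule, first scan.** Cycle 2 days 14–21 (3.8.2 footnote 7) are study days 35–42, or 34–41 elapsed. Lag 7: 7/48 = 14.6% to 7/41 = 17.1%. Lag 28: 28/69 = 40.6% to 28/62 = 45.2%.
- **5-day schedule, second scan.** Cycle 4 days 14–21 are 76–83 elapsed. Lag 7: 7/90 = 7.8% to 7/83 = 8.4%. Lag 28: 28/111 = 25.2% to 28/104 = 26.9%.
- **10-day schedule, first scan by 3.1.** Days 26–35 are 25–34 elapsed. Lag 7: 7/41 = 17.1% to 7/32 = 21.9%. Lag 28: 28/62 = 45.2% to 28/53 = 52.8%.
- **10-day schedule, first scan by 6.2.1.** Day 28 ± 3 is 24–30 elapsed. Lag 7: 7/37 = 18.9% to 7/31 = 22.6%. Lag 28: 28/58 = 48.3% to 28/52 = 53.8%.

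At lag 0 every share is 0%. Actual lags may be only days.

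**The case against.** The strongest reply is that this is an obvious one-letter slip. The section is headed for progression, progression is fully defined in 6.2.2 and 6.2.3, and 3.1 follows patients to documented progression. Putting 'or' for 'of' makes the sentence grammatical. The other candidate, 'date' for 'death', reads less naturally. This largely stands, and a reader should not infer that the investigators mean to ignore progression. It does not dispose of the point: with 'or', the definition is PFS while 1.1.2, 6.2.4 and section 8 still say TTP. The same mismatch remains if the source file turns out to print 'or'.

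A reader might also infer that later cancer deaths would go unrecorded, because beyond 30 days after the last dose 7.3 tells investigators to "only report those that have an attribution of at least possibly related to the agent/intervention". The documents do not support that. Section 7.3 governs reporting to the IND sponsor. Section 7.2.2 also asks for all Grade 5 and all serious events at continuing review, whatever their attribution. Progression is a reason to stop treatment (3.10.1) but is not listed as a reason to leave the study (3.10.2), and death is an off-study reason. A later death can therefore be recorded. What is missing is scheduled survival follow-up.

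On the origin, a reader might infer that counting from consent is an error or that the lag has no limit. Neither follows. In a single-arm exploratory endpoint a consent origin is a legitimate convention and biases no comparison. Section 2.2 requires screening within 28 days before any study intervention, and 2.3 requires registration of an eligible candidate within 24 hours of consent. Those rules bear on the lag without stating it.

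**Conclusion.** The definition in 6.2.4 is wrong as written. Taken literally, it has the wrong event for its name and does not fit the follow-up schedule. Repaired in the likeliest way, it has the wrong name for its event. That 'of' is a slip for 'or' is an inference, though a strong one; the conclusion that event and label need reconciling does not depend on it.

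The size is minor. TTP is secondary and exploratory, with no test, threshold or comparator. No planned number changes, and DLT, MTD, expansion and accrual do not use it. The harm is confined to what the reported times mean. The difference in origin is a consistency point only, and the lag shares above rest entirely on assumed lags.

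**What to change.** Rewrite 6.2.4 in one of two ways.

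(a) Keep TTP: time to first documented progression under 6.2.2 or 6.2.3. Censor deaths without documented progression, and patients without an event, at the last tumor assessment, and report the number of such deaths.

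(b) If deaths are meant to count: time to progressive disease or death from any cause, with patients without an event censored at the last tumor assessment. Rename the endpoint PFS in 1.1.2, 6.2.4 and section 8.

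Secondary suggestion for either option: start the clock at the first rhIL-15 infusion, to match 6.2.2.6 and 6.2.2.7.

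The cost is one sentence, plus the label under (b). No visit, scan or patient is added: the infusion start is already needed to time the PK samples (5.1.1), and restaging is already planned (3.1, 3.8.2, 6.2.1). There are two downsides. With the new origin, each reported time shortens by that patient's consent-to-dose lag. Under (a), censoring deaths that are in fact disease-related can make TTP look longer, which is why their number should be reported.
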